6.3.3 Storage, Packaging, Dispensing, Reconciliation, and Return of Supplies

TOOKAD® Soluble will be supplied by the Sponsor as vials containing 200 mg or 400 mg of powder for solution for injection. In compliance with local laws and with Good Manufacturing Practices (GMP) boxes will be labelled in the local language in the country of administration, including at least the following information:

1. Sponsor name and address,
2. Study reference number,
3. Treatment number,
4. Name of Principal Investigator,
5. Name of drug,
6. Dose and formulation,
7. Administration method,
8. Batch number,
9. Expiry date (day/month/year) and
10. Legal notes.

The study medication will be stored in a secure area maintained at 2°C to 8°C, under the responsibility of the pharmacist. Only personnel properly informed of preparation procedures will be permitted to dispense study medication. The process for drug preparation will be under the responsibility of the study site Pharmacist. In case of temperature excursion the pharmacy will notify the Sponsor or designee within 48 hours and place the drug under quarantine until the Sponsor has given a written approval to use the drug.

All supplies shipped to site must be properly accounted for. Upon receiving study medication the pharmacist will immediately return the acknowledgement receipt to the Sponsor or the Sponsor's designee; this receipt records the signature of the person receiving the study medication and the date received.

The pharmacist responsible for dispensing the study medication will receive a drug dispensing schedule. The Investigator should keep accurate records regarding the dispensing and return of study medication and any departure from the expected dispensing or return of study medication must be recorded.

At the termination of the study the Drug Accountability Record will be completed. All study medication (used and unused), in its packaging, will be returned to the Sponsor unless written approval from the Sponsor authorizing the destruction. Unused bottles are to be kept refrigerated and protected from light until instructions from the Sponsor or the Sponsor's designee.

6.3.4 Procedures carried out in the operating-room

Light delivery catheter insertion:

Subjects will be placed in the lithotomy position and will remain in this position throughout the procedure. A Foley catheter is placed in the bladder prior to the procedure, and removed at least 6 hours after the procedure. TRUS images are used to visualize the prostate and to define the treatment guidance using TOOGUIDE TRUS.

A transperineal template is used to guide the placement of the flexible hollow introduction catheters into the prostate. These have a metal inner mandrel to aid insertion. This procedure is similar to that used routinely for high dose rate (HDR) brachytherapy of prostate cancer.

Following satisfactory positioning of the introduction catheter the metal mandrel is removed and replaced with a cylindrically diffusing optical fiber. The length of the diffusing part of the fiber is chosen according to the treatment guidance based on the ultrasound images of the prostate. Fibers are available with illuminating fiber lengths of 1 - 5 cm, in 0.5 cm increments.

Laser:

The lasers to be used for the procedure (Intermedic, Spain) are connected to the optical fibers, once the optical fibers are satisfactorily positioned within the flexible introduction catheters.

Light detection:

One light detecting probe will be placed in the rectum to ensure that the light dose is sufficiently low. The prostate is illuminated prior to drug injection and the light measured. If the light in the rectum exceeds 13 mW/cm² then the optical fibers in the prostate will be repositioned.

Drug delivery:

The infusion puncture site should be placed in a large vein at the top of the forearm. The infusion will be conducted using automatic syringes, through a fast flow peripheral line (antecubital catheter). The Sponsor will provide the study centre with the appropriate infusion devices. Infusion will be over 10 minutes. The choice for size of intravenous catheter will be left up to the discretion of the involved medical

team who will be responsible for ensuring that the catheter is flushed and working properly prior to starting infusion.

Light delivery:

The light delivery will begin once the drug infusion has ended. Light will be delivered at an energy dose of 200 J/cm with a power of 150 mW/cm over 22min 15s.

See appendix 6 "VTP procedure Book".

6.3.5 Light Protection Following TOOKAD® Soluble Administration

Instructions for light protection following TOOKAD® Soluble administration are found in Appendix 3. In the recovery room and ward, dim general lighting should be used. Blinds should be utilised to prevent sunlight exposure and direct reading lamps will not be used. If dim lighting cannot be achieved, then local screens should be placed around the subject. If the subject reports any discomfort to the skin or eyes during hospitalisation, the general level of lighting must be reduced and extra care taken to shield both artificial and natural light.

6.3.6 Prevention of Thrombosis Following VTP

The risk of thromboembolic events is known to be increased following general anaesthesia, and especially when it is associated with pelvic surgery for cancer. Therefore, prophylactic measures will be taken to avoid such events.

The choice of the measures for the prevention of thromboembolism is left at the discretion of the investigator, as per local clinical standards [e.g., subcutaneous injection of low molecular weight heparin (LMWH), pneumatic compression devices].

6.3.7 Concomitant Medication

Previous medication (started before the screening visit) and concomitant medication (started at the screening visit or up to the last visit, whether there is continued use or not) must be identified in the subject's medical record, including all the medication administered with TOOKAD® Soluble -VTP and in the immediate post-procedure period. These medications will be recorded on the electronic case report form (eCRF).

For each medication taken, the following information will be collected:

1. Medicine trade name (including dose and frequency),
2. Indication for which the medication was prescribed,
3. Date started and Date stopped.

6.3.8 Prohibited Concomitant Medication

1. Medications which have potential photosensitising effects (such as tetracyclines, sulphonamides, quinolones, phenothiazines, sulfonylurea hypoglycaemic agents, thiazide diuretics, griseofulvin or amiodarone) should be stopped at least 10 days before and for 3 days after the TOOKAD® Soluble -VTP procedure or replaced by other treatments without photosensitizing properties. If it is not possible to stop a photosensitising medicinal product (such as amiodarone), the patient should be advised that increased sensitivity to sunlight may occur and they may need to protect themselves from direct light exposure for a longer period.
2. Anticoagulant drugs (e.g., warfarin) are prohibited if they cannot be stopped at least 10 days before the TOOKAD® Soluble- VTP procedure.
3. Compounds that decrease clotting, vasoconstriction, and platelet aggregation (e.g. aspirin) should be stopped at least 10 days before and for 3 days after the TOOKAD® Soluble- VTP procedure.
4. OATP1B1 and OATP1B3 transporter substrates: The magnitude of interaction has not been investigated clinically but a transient increase in the plasma concentration of co-administered substrates of OATP1B1 and OATP1B3 (e.g. statins) cannot be ruled out. The use of medicinal products that are substrates of OATP1B1 or OATP1B3 for which concentration-dependent serious adverse events have been observed should be avoided on the day of TOOKAD® Soluble infusion and for at least 24 hours after administration. Co-administration should be done with caution and close monitoring is recommended.
5. A list of prohibited medications is provided in Appendix 10.

6.3.9 Laser storage

The lasers (Intermedic) and a user manual will be supplied by the Sponsor. The lasers will be stored in an appropriate locked room, under the responsibility of the site Investigator. The Sponsor will provide a qualified, experienced laser operator to attend all TOOKAD® Soluble- VTP procedures and train assigned on-site personnel in the use of the laser, until this training has been completed and the site has the required expertise to operate the laser.

6.4 Elements of Study Process – Study visits

6.4.1 Visit 1 (V1) and screening period

Apart from the patient's file review and information of the patient about the study, no study related procedure should be done or prescribed before the patient has signed the Patient Informed Consent Form (PICF).

1. Review of existing prostate biopsy
2. Review inclusion/exclusion criteria
3. Informed consent
4. Medical history
5. TNM staging
6. Digital rectal examination
7. Prostate volume
8. IPSS and IIEF questionnaires
9. Concomitant medication, and review of prohibited medication (see Appendix 10)
10. Clinical examination including vital signs (blood pressure and pulse rate)
11. Blood sample for laboratory evaluations including PSA or review of existing laboratory results if available in the patient file before he was considered for inclusion in the study, and done not more than 4 weeks before visit 1.
12. MRI

6.4.2 Visit 2 (V2): TOOKAD® Soluble VTP procedure

Subjects will come to the unit on the day of the procedure, having fasted per institutional standards in preparation for anaesthesia. After the TOOKAD® Soluble- VTP treatment, they will remain in the clinical unit under medical and nursing supervision for at least 6 hours after TOOKAD® Soluble infusion. The subject will be kept under medical surveillance in a dimmed room for at least 6 hours after the procedure and may be discharged in the evening of the procedure day. Depending on the duration of the anaesthesia and the patient condition, the investigator can decide to keep him hospitalised overnight. In this case, the patient may be discharged in the following morning. Further need for inpatient based hospital care will be based on the patient's condition and medical needs as determined by the treating physician. Post-procedure hospitalization is expected to vary from approximately 6 to 24 hours. If for any reason other than those listed above (i.e., distant home) the investigator decides to keep the patient overnight, such

reason is to be recorded in the CRF, and a mention is to be made that the patient could have been discharged in the evening of the procedure day.

Prior to Anaesthesia:

1. Concomitant medication
2. AEs recording
3. Vital signs (blood pressure, pulse rate and body weight)
4. Blood collection for laboratory testing and PSA testing

After anesthesia has been induced, anesthetic monitoring is to be done according to institutional clinical practice guidelines. Patients are to be placed in the lithotomy position and to remain in this position during the procedure. During the procedure, the patient's skin and eyes are to be protected from the operating room surgical lights with opaque drapes.

After the VTP procedure, the following procedures and assessments are to be made:

1. Recording of adverse events (AEs)
2. Performance of clinical examination
3. Assessment of concomitant medication
4. Blood samples for laboratory and PSA testing 4 to 6 hours following the procedure
5. Removal of catheter

The subject is then discharged from the hospital, unless there are medical reasons that require prolonged hospitalisation.

6.4.3 Visit3 (V3): Day 7 +/- 2 days

Subjects will come to the unit seven days after the procedure for the following assessments:

1. Recording of AEs
2. Assessment of concomitant medication

6.4.4 Visit 4 (V4): Month 1 (± 1 week)

1. The procedures for this assessment are: Blood collection for laboratory testing and PSA testing
2. Recording of AEs
3. Collection of IPSS and IIEF questionnaires
4. Assessment of concomitant medication

6.4.5 Visit 5 (V5): Month 3 (±2 weeks)

The procedures for this assessment are:

1. Multiparametric MRI of the prostate with contrast. The procedure for this MRI is described in Appendix 2
2. Blood collection for laboratory and PSA testing
3. Performance of prostate biopsy
4. Recording of AEs
5. Assessment of concomitant medication
6. Collection of IPSS and IIEF questionnaires

6.4.6 Visit 6 (V6): Month 6 (±2 months)

The procedures for this visit are:

1. Blood collection for laboratory testing and PSA testing
2. Recording of AEs
3. Assessment of concomitant medication
4. Collection of IPSS and IIEF questionnaires

6.4.7 Visit 7 (V7): Month 12 (±2 months)

The procedures for this visit are:

1. Blood collection for laboratory and PSA testing
2. Recording of AEs
3. Assessment of concomitant medication
4. Collection of IPSS and IIEF questionnaires
5. Performance of prostate biopsy
6. MRI

6.4.8 Visit 8-10 (V8-V10) Months 24 (± 3 months), 36 (± 3 months), 48 (± 3 months)

1. Blood collection for laboratory and PSA testing
2. Recording of AEs
3. Assessment of concomitant medication
4. Collection of IPSS and IIEF questionnaires

5. Performance of prostate biopsy, as indicated per institutional standard of care
6. MRI, as indicated per institutional standard of care

6.4.9 Visit 11 (V11) Months 60 (\pm 3 months) – End of study visit

1. Blood collection for laboratory and PSA testing
2. Recording of AEs
3. Assessment of concomitant medication
4. Collection of IPSS and IIEF questionnaires
5. Performance of prostate biopsy, as indicated per institutional standard of care
6. MRI, as indicated per institutional standard of care

6.4.10 Additional Visits

A single re-treatment of lobes found positive for cancer at 3-months follow-up is allowed.

Those additional treatments will be performed in the same conditions as for the first VTP procedure (section 6.4.2.). The schedule of visits will remain unchanged and the whole study duration will be sixty months.

6.4.11 Post-procedure or follow-up assessments

Based on the results of post-procedure or follow-up assessments, or upon decision by them or their clinician, patients may at any time decide to undergo additional radical therapy.

7 OUTCOMES ASCERTAINMENT

7.1 Prostate biopsy

All subjects will undergo biopsy at 3 and 12 months according to protocol. The need for subsequent biopsy beyond 12 months will be at the discretion of the investigator according to standard of care. All biopsy procedures will consist of a transrectal ultrasound guided prostate biopsy with a minimum of 12 cores and include both lobes of the prostate gland. Any suspicious volumes meeting PIRADS (version 2) criteria of level 4 or 5 found on MRI will be targeted with at least 2 cores taken from each suspicious lesion. Patients will undergo pre-biopsy preparation using standard of care practices for the institution that should include the use of peri-procedural antibiotics. Patients who fail to receive antibiotics for the biopsy procedure will be considered a violation.

Anatomopathological reports will include:

1. The number and length of cores taken,

2. The number and the location of cores with cancer,
3. The cancer core length (CCL) which is linear millimeters of cancer on each core and the percentage of cancer on each core,
4. The Gleason grading of each core.

7.2 Patients' questionnaires on erectile dysfunction and urinary symptoms

The following questionnaires will be applied to all patients to assess erectile function and urinary symptoms at entry and at months 1, 3, 6, 12, 24, 36, 48 and 60:

- IIEF-15 for erectile function

The International Index of Erectile Function (IIEF) relates to the following areas: confidence in erection; erection sufficient for penetration; maintaining of erection; difficulty to maintain erection for completion; satisfactory intercourse. Subjects will be asked to give their response to each of the areas using a 6-point scale (0=no sexuality, 5=best response).

- IPSS for lower urinary tract symptoms

The International Prostate Symptom Score (IPSS) is an 8-question questionnaire focused on urinary symptoms with one general question about urinary symptoms. The questions relate to the following areas: sensation of bladder emptying; frequency of urination; stops when urinating; difficulties to postpone urination; urinary steam; beginning of urination; night urination. Subjects will be asked to give their response to each of the areas using a 6-point scale (0=none or normal, 5=worse response).

These questionnaires will encompass the consequences of all treatments, including additional radical therapy potentially used by patients. Scores for each one of the scales will be calculated regardless of failure or not, and additional treatment or not.

8 ADDITIONAL ASSESSMENTS

8.1 Assessment of Clinical Signs of Suspected Rectal, Urethral or Bladder Injury

For suspected rectal, urethral or bladder injury, imaging studies should be performed as appropriate, with direct visualisation (cystoscopy and proctoscopy) performed when clinically necessary. In cases where such procedures are performed during the time of the protocol, photographic documentation of findings should be obtained when possible and maintained with the patient's records with de-identified copies made available upon request to the Sponsor. For subjects with confirmed injury, standard clinical care including referral to a specialist for corrective procedure and/or surgery will be performed. Clinical signs should be followed up at each subsequent study visit until resolution of the injury has been confirmed.

8.2 Post Treatment MRI

Prostate MRI

MRI of the pelvis and prostate gland will be performed at 3 months and 12 months following VTP treatment. Additional MRI may be performed at the discretion of the investigator up to 60 months. Results from these studies are used to confirm expected treatment effects to the prostate gland as well as evaluate for any extra-prostatic tissue changes that may be associated with side effects and find any suspicious lesions within the prostate. Any suspicious volumes meeting PIRADS (version 2) criteria of level 4 or 5 found on MRI will be targeted with at least 2 cores taken from each suspicious lesion. Additional clinically actionable findings identified on MRI will be left to the discretion of the treating physician. Lymph nodes that are 15 mm in diameter or smaller in size will be considered negative by convention although may be biopsied at the discretion of the physician. Lymph nodes greater than 15 mm in diameter will be considered suspicious by convention and will require biopsy confirmation of cancer to be classified as metastases.

8.3 Laboratory Assessments

Choice of the laboratory

A local laboratory will be used for safety biological parameters and PSA testing.

Laboratory examinations

The following laboratory tests should be prescribed at Visit 1 and their results should be available for eligibility assessment prior to the VTP procedure. If similar laboratory tests are available in the patient file before the patient is considered and approached for his entry in the study, the results of these test can serve as the eligibility assessment and do not need to be repeated, provided they have not been done more than 4 weeks before visit 1.

At any time during the study, for safety reasons, and when in the patient's best interest, additional tests may be performed at the discretion of the Investigator.

If one of the result of the laboratory tests (eg PSA levels) done after consent signature do not meet the inclusion/exclusion requirements, it can be repeated at the discretion of the investigator, but not more than twice.

Screening (V1) blood tests:

- Standard hematologic tests
- Standard blood chemistry tests
- Standard Blood Coagulation Tests

- Additional inclusion blood tests
- PSA

Blood tests to be taken during the during Visit 2 both before and after the TOOKAD® Soluble VTP procedure as well as taken 1, 3, 6, 12, 24, 36, 48 and 60 months after the VTP procedure:

- Standard hematologic tests
- Standard blood chemistry tests
- PSA

Standard hematologic tests:

Hemoglobin, Red cell count, M.C.V., Hematocrit, M.C.H., White cell count, Differential white cell count (%), Platelet count.

Standard blood chemistry tests:

Sodium, Potassium, Chloride, Bicarbonate, Calcium, Creatinine, Urea, Glucose, Total Protein, Albumin, Alkaline Phosphatase.

Standard Blood Coagulation Tests:

INR (pro-time), aPTT.

Additional inclusion blood tests:

Alanine Aminotransferase (ALAT/SGPT) and Aspartate Aminotransferase (ASAT/SGOT)

PSA:

Prostate Specific Antigen

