- Patients' reported outcome measures (PROMs) impairment: urinary symptoms using IPSS and erectile functions using IIEF prior to treatment beginning and then 1, 3, 6, 12, 24, 36, 48 and 60 months after completing treatment
- Severe prostate cancer-related events: cancer extension to T3, metastasis or prostate cancer-related death
- Use of secondary prostate cancer treatment following VTP will include surgical removal of the prostate gland, radiation treatment to the prostate gland, use of hormone or chemotherapies.
- Adverse events
- Serum PSA measurements in ng/mL.

SAMPLE SIZE JUSTIFICATION

A proportion of responders of $r=70\%$ at 12 months is considered to be a clinically significant expectation in localized intermediate-risk prostate cancer patients.

Based on historical data in similar series of patients, a minimum of $N=44$ patients is required to test the null hypothesis $H_0: "r \leq 70\%"$ vs. $H_1: "r > 70\%"$, with 80% power and 5% as alpha risk.

MANUFACTURING INVESTIGATIONAL PRODUCT:

TOOKAD® Soluble is manufactured by Praxis Pharmaceutical S.A, Vitoria-Gasteiz, Spain.

TOOKAD® Soluble batches are released by Steba Laboratories, Ness Zion, Israel.

Laser equipment: Intermedic Arfran S.A, Spain

FLOW CHART: Schedule of Events

Procedure	V1 and screening period	V2 VTP	V3 Day 7+/- 2 days	V4 Month 1 +/- 1 wk	V5 Month 3 +/- 2 wks	V6 Month 6 +/- 2 mos	V7 Month 12 +/- 2 mos	V8-11 Annual f/u +/- 3 mos
Informed Consent	X							
Inclusion/exclusion Criteria	X							
Medical History	X							
TNM Staging	X							
VTP Treatment		X						
Clinical Examination	X	X ^a						
Prostate Biopsy	X ^b ≤6mos before consent				X ^c		X	X ^d
Digital Rectal Examination	X							
Prostate Specific Antigen	X ^e	X		X	X	X	X	X
Standard Hematologic Tests	X ^e	X ^a		X	X	X	X	X
Standard Blood Chemistry Tests	X ^e	X ^a		X	X	X	X	X
Standard Blood Coagulation Tests	X ^e							
Additional Inclusion Blood Tests	X ^e							
Prostate Volume	X	X						
MRI	X ^d				X		X	X ^d
Patient-Reported Outcome Measures (PROMs)	X			X	X	X	X	X
Study Medication		X						
Concomitant Medications	X	X ^a	X	X	X	X	X	X
Adverse Events		X ^a	X	X	X	X	X	X

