5.4 Surgery and other Treatment-Related Conditions of Exclusion

Any condition or history of illness or surgery that may pose an additional risk to men undergoing the TOOKAD® Soluble -VTP procedure such as:

1. Any condition or history of illness or surgery that in the opinion of the investigator might affect the conduct and results of the study or pose additional risks to the subject (e.g., cardiac or respiratory disease precluding general anesthesia; anticoagulant treatment which cannot be temporarily withdrawn for the procedure).
2. Medical conditions that preclude the use of general anesthesia;

3. Any condition or history of active rectal inflammatory bowel disease or other factors which might increase the risk of fistula formation;
4. Hormonal manipulation (excluding 5-alpha-reductase inhibitors) that alters androgen production, within the previous 6 months;
5. History of urethral stricture disease;
6. History of acute urinary retention within 6 months of study entry;
7. Anticoagulant drugs (e.g., warfarin) that could not be withdrawn during the 10 days prior to the VTP procedure or antiplatelet drugs (e.g. aspirin) that could not be withdrawn during the 10 days prior to the VTP procedure and 3 days after VTP;
8. Renal and hepatic disorders with values of >1.5 times the upper limit of normal (ULN) or blood disorders (upon clinician judgment);
9. A history of sun hypersensitivity or photosensitive dermatitis.

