**Clinical laboratory evaluation**

Laboratory values will be individually listed by patient number. Values outside the laboratory reference ranges will be flagged on these individual data tables. The investigator will assess whether the values outside of the reference ranges are clinically significant or clinically non-significant. Lab abnormalities will be graded using the NCI Common Terminology Criteria for Adverse Events.

For those parameters that can be graded according to the NCI Common Terminology Criteria for Adverse Events, summaries of shift from baseline in toxicity grade to each post-baseline visit will be provided.

For those parameters that cannot be graded, frequencies of patients' transitions between normal and abnormal not clinically significant (NCS) and abnormal clinically significant (CS) categories will be tabulated.

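### No ALT, AST or bilirubin is scheduled after VTP, so hepatocellular injury would surface only through symptoms or discretionary tests, and no ALT/AST recheck is scheduled before a second VTP.

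*Protocol*

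**What the plan says.** Exclusion 8 in protocol section 5.4 (repeated in the Synopsis) bars men with "Renal and hepatic disorders with values of >1.5 times the upper limit of normal (ULN"). It names no analyte.

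Section 8.3 defines the laboratory groups by explicit lists:

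- The standard chemistry panel is "Sodium, Potassium, Chloride, Bicarbonate, Calcium, Creatinine, Urea, Glucose, Total Protein, Albumin, Alkaline Phosphatase". Alkaline phosphatase and albumin are in it; ALT, AST and bilirubin are not.
- ALT and AST are the only content of the additional inclusion tests. Section 8.3 lists that group under screening alone, and the flow chart row "Additional Inclusion Blood Tests" carries one mark, at Visit 1.
- Haematology, the chemistry panel and PSA are drawn before and after the procedure at Visit 2, "as well as taken 1, 3, 6, 12, 24, 36, 48 and 60 months after the VTP procedure".

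Section 8.3 also lets the investigator order extra tests at any time for safety reasons.

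For a second VTP, section 6.4.10 says: "Those additional treatments will be performed in the same conditions as for the first VTP procedure". It points to section 6.4.2, whose pre-procedure and post-procedure bloods are the Visit 2 set. The visit schedule is otherwise unchanged.

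The SAP (Clinical laboratory evaluation) says that, for parameters that can be graded by CTCAE, "summaries of shift from baseline in toxicity grade to each post-baseline visit will be provided".

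**The concern.** The protocol sets a hepatic limit at entry and measures two transaminases that appear to serve it. It then schedules neither again for 60 months, although blood for other chemistry tests is taken throughout.

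Three things are at stake:

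- **Detection.** Section 9.2 asks for general questioning and says specific events should not be solicited. A silent transaminase rise would therefore appear only if someone chose to test for it.
- **Reporting.** The SAP's shift tables compare baseline grade with grade at each later visit. For ALT and AST the second half of that comparison has no scheduled data. This also affects the SAP's separate safety analysis of re-treated men.
- **Re-treatment.** Section 6.2.3 makes a second VTP conditional on no earlier grade 3 or 4 adverse event, and section 9.1 counts abnormal laboratory findings as adverse events. A transaminase abnormality can enter that judgement only if it has been measured.

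**Working it through.** The plan states no figure on this point to reproduce. The check is a count of scheduled draws, a calculation of elapsed time, and an illustration of what systematic testing would provide.

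**1. Scheduled values per man, treated once** (section 8.3 and flow chart)

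| Time | Standard chemistry | ALT/AST |
|---|---|---|
| Visit 1 | 1 | 1 |
| Visit 2, before VTP | 1 | 0 |
| Visit 2, after VTP | 1 | 0 |
| Months 1, 3, 6, 12, 24, 36, 48, 60 | 8 | 0 |
| Total | 11 | 1 |
| After treatment | 1 + 8 = 9 | 0 |

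The pre-VTP draw at Visit 2 is not counted as post-treatment. The SAP defines baseline as the last value reported until the treatment date, so that draw belongs to baseline. A re-treated man has 2 further draws (before and after the second VTP, carried over from section 6.4.2), again without ALT/AST.

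**2. Age of the last scheduled ALT/AST at a second VTP**

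- Month 3 biopsy window: 3 months ± 2 weeks (flow chart, section 6.4.5).
- Re-treatment: 2 to 4 months after that biopsy (Synopsis, Treatment Conditions).
- 2 weeks = 2 × 12/52 = 0.46 month.
- Nominal time since first VTP: 3 + 2 = 5 to 3 + 4 = 7 months.
- With the window: 3 − 0.46 + 2 = 4.5 to 3 + 0.46 + 4 = 7.5 months.

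These are minimum ages, because the value was taken at or before Visit 1. The interval from Visit 1 to the first VTP comes on top and has no stated maximum. So do up to 4 weeks (4 × 12/52 = 0.9 month) if a result already in the patient file was accepted.

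**3. What systematic testing of 50 men would give**

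The Synopsis plans 50 treated men. The documents give no transaminase event rate, so the rates below are assumptions. The chance of at least one event is 1 − (1 − p)^50:

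| Assumed true rate p | Chance of seeing at least one event in 50 |
|---|---|
| 2% | 1 − 0.98^50 = 64% |
| 5% | 1 − 0.95^50 = 92% |
| 10% | 1 − 0.90^50 = over 99% |

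If all 50 were tested and none had an event, the one-sided exact 95% upper bound would be 1 − 0.05^(1/50) = 5.8%. With tests done only on suspicion, there is no tested denominator for such a bound.

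**The case against.** A reader might infer that liver injury cannot be seen at all and that the hepatic limit cannot be rechecked. The documents do not support that. Section 8.3 allows additional safety tests at any time. Alkaline phosphatase, albumin and total protein are repeated at Visit 2 and all eight later blood visits. Adverse events, including abnormal laboratory values, are followed for 60 months. This stands: the gap is in scheduled hepatocellular testing, not in all hepatic observation. It does not rescue the analysis, because values ordered on suspicion come from a selected group and cannot fill a shift table for all men.

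A reader might also infer a direct contradiction between sections. That is too strong. Exclusion 8 is an entry criterion and names neither ALT nor AST; the link to them is inferred from their label as inclusion tests. INR and aPTT are also taken at screening only, so entry-only testing is a consistent pattern. The SAP sentence on shifts names no analyte and can be read as covering whatever is collected. No section says in words that the hepatic limit applies again before a second VTP. All this stands, and it makes the point one of ascertainment and clarity.

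Nor do the documents show that the drug injures the liver. In section 2.2.3.2 palladium was measurable in rat liver only at the first sampling times, and in other tissues too. Section 2.2.3.3 reports that no target organ was identified in the 4-week rat study. The OATP1B1/1B3 text in section 6.3.8 warns about levels of co-administered drugs. The clinical summaries in section 2.2.4 mention no hepatic signal, and the Investigator's Brochure is not available here.

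Finally, the safety objective is to describe adverse events, section 10.5 lists adverse events and clinical examination, and no hepatic claim is planned. That limits the consequence. Section 9, however, includes laboratory assessments among the safety evaluations, and the SAP gives them their own section.

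**Conclusion.** The point holds in a limited form. Followed as written, the plan yields 0 post-treatment ALT/AST values per man against 9 post-treatment draws for the other chemistry tests. Bilirubin is not scheduled at any time. Hepatocellular injury would be found only through symptoms or discretionary testing, and the SAP's shift tables would have no scheduled ALT/AST data. No ALT/AST recheck is scheduled before a second VTP, when the last scheduled value predates the first dose and is at least about 4.5 to 7.5 months old.

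This rests on reading the lists in section 8.3 as complete and on section 6.4.10 carrying over only the Visit 2 laboratory set. It assumes nothing about whether the drug affects the liver. The primary endpoint, analysis populations and error rates are untouched. An absence of reported transaminase events would not be evidence of hepatocellular safety.

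**What to change.** 1. Add ALT and AST to the chemistry panel in section 8.3, run on blood already drawn at Visit 2 (before and after VTP) and at Months 1, 3, 6, 12, 24, 36, 48 and 60. Include the pre-procedure and post-procedure draws that section 6.4.10 carries over to a second VTP. Scheduled results per man treated once rise from 1 to 11, of which 9 are post-treatment.
2. Reconcile section 5.4, sections 6.4.2 and 6.4.10, section 8.3, the flow chart and the SAP. State which tests exclusion 8 refers to and whether it applies at entry only. That choice is the sponsor's; no threshold or management rule is proposed here.
3. Name in the SAP the analytes that enter the shift tables, and list discretionary results separately from scheduled ones.
4. If the assays are not added, say in the SAP and the report that transaminases after VTP were not systematically assessed and that no conclusion on hepatocellular safety can be drawn.

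The cost is small: at most 50 men × 10 draws × 2 assays = 1,000 assay results over the whole study, apart from re-treatments, with no new visit or blood draw.
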